## 6.12 Clinical Laboratory Tests (Safety)

Safety laboratory tests will be performed at the time points specified in Table 3 and sent to a Central Laboratory. Blood samples sent to the local laboratory for the purposes of determining study eligibility must be repeated and sent to the central laboratory following enrollment. Collect blood and/or urine at LFU only if the subject had an abnormal (high/low flag) result at TOC. Additional tests may be performed at the discretion of the Investigator if deemed clinically appropriate. Subjects treated as outpatients must agree to return to the site for blood draws.

A full list of the clinical laboratory tests that will be performed and analyzed can be found in Appendix 1. A pregnancy test will be performed on all females who are not surgically sterile

or post-menopausal for at least 2 years. A negative urine pregnancy test is required prior to randomization and must be confirmed as soon as possible using a serum pregnancy test.

Any safety laboratory results outside the normal range will be repeated at the discretion of the Investigator and will be evaluated by the Investigator or designee as “clinically significant” or “not clinically significant.” Any clinically significant value should be repeated as necessary and followed until resolution.

### 6.13 Sample Collection for Pharmacokinetic Analysis

Blood samples for PK analysis of lefamulin and its main metabolite, BC-8041, in plasma following IV dosing will be collected in association with the morning dose of study drug on Study Day 3 as specified in Table 9 below.

**Table 9. Sample Collection Time Points for the Determination of Lefamulin Plasma Concentrations following IV Infusion**

Sample Time	Day 3 (morning dose)
Within 1 h prior to the morning infusion of study drug	X
Within 10 minutes following the end of infusion	X
2-4 h following the end of infusion	X
8-12 h following the end of infusion	X

In a subset of subjects, after switching from IV to oral treatment, blood samples for PK analysis will be collected relative to the first morning dose of **oral** drug as specified in Table 10 below. Blood sampling for PK analysis following oral dosing will be optional, and will be limited to subjects who agree via written consent, and for whom the additional blood collection is logistically feasible.

Outpatients who have consented for oral drug PK samples will return to the clinical site for PK blood collection relative to the first morning dose of oral drug. These subjects should be instructed to not take their first morning dose of study drug at home that day, rather to bring all blister packs (used and unused) to the study site. Following collection of the pre-dose blood sample, subjects will take their dose of study drug under supervision of study personnel, and subsequent PK blood samples will be collected.

**Table 10. Sample Collection Time Points for the Determination of Lefamulin Plasma Concentrations after Switch to Oral Treatment**

Sample Time	1 st oral morning dose after switch
Within 1 h prior to 1 st morning dose of oral study drug ( $C_{min}$ )	X
1-3 h after oral drug administration	X
4-8 h after oral drug administration	X

NOTE: For all subjects it is essential to record the exact date and actual time of each study drug administration for all IV doses as well as for the 1st oral dose. Additionally, for subjects who have blood collected for PK in association with the first morning oral dose, it is essential to record the exact date and actual time of all oral doses up to and including the PK sampling dose. Documentation of the exact blood sampling time points for population PK analysis is also essential (see Section 5.10 – Adherence).

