**Figure 1. Study Design Overview – CABP not caused by MRSA**

- a: IV treatment will be initiated with 1 infusion q12h. All infusions will be blinded. While receiving IV treatment, subjects in the moxifloxacin treatment arm will receive moxifloxacin q24h alternating with saline placebo q24h to maintain the blind.
- b: All subjects will have IV treatment for a minimum of 3 days (6 doses) after which time IV treatment may be changed to oral if pre-defined criteria are met.

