- w: Study drug should be administered approximately the same time each day. On days when this is not feasible, doses should be given within 4 hours of the scheduled dosing time (i.e., a minimum of 8 hours between doses). Subjects who receive only a single dose of study drug on Day 1 will receive their final dose in the morning on either Day 8 (to complete a 7-day course) or on Day 11 (to complete a 10-day course). Administration of study drug may occur on the same calendar day as EOT, and if so will be completed before EOT assessments begin.
- x: Collect blood for PK analysis in association with the morning dose of IV study drug on Day 3. Collect blood for PK samples within 1 h before administration of IV study drug, within 10 minutes following completion of the infusion, at 2–4 h after infusion, and at 8–12 h after the infusion. In subjects who agree via written consent, and for whom collection is logistically feasible, blood for PK analysis will be collected in association with the first morning dose of oral study drug. Blood will be collected within 1 h prior to dose, 1–3 h after dose, and 4–8 h after dose. Since blood collection is required both before and after the first morning oral dose, outpatients should be instructed to not take their first morning dose of oral study drug at home, rather to bring all blister packs (used and unused) to the study site. Following collection of the pre-dose blood sample, subjects will take their dose of study drug under supervision of study personnel, and subsequent PK blood samples will be collected.
- y: Investigator to determine IACR - Success, Failure or Indeterminate (i.e., subject lost to follow up) at EOT and TOC and Sustained Success, Relapse or Indeterminate at LFU. The Investigator will not determine Clinical Response at TOC or LFU if the subject was previously deemed to have an IACR of Failure.
- z: Collect pleural fluid samples and/or BAL only if medically indicated. Gram's stain samples, culture, and test the isolated pathogens for susceptibility. Pathogens isolated from pleural fluid and/or BAL samples will be sent to the central laboratory for confirmatory identification and susceptibility testing. If possible, pleural fluid samples should be incubated in blood culture bottles for optimal pathogen recovery.

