## 5.6 Timing of Dosing and Dose Administration

Blinded IV study drug (lefamulin, moxifloxacin, linezolid, and matching placebo) will be administered approximately every 12 hours. Blinded IV lefamulin and moxifloxacin study drug doses will be infused over approximately 60 minutes. Blinded IV linezolid and matching placebo will also be infused over approximately 60 minutes. In subjects with suspected or confirmed MRSA, IV lefamulin and IV linezolid placebo or IV moxifloxacin and IV linezolid may be administered concurrently if two separate IV lines are used. If only one IV line is used, IV lefamulin and moxifloxacin should always be infused prior to linezolid or matching placebo.

The first dose of study drug will be administered on Day 1, as soon as possible after the diagnosis of CABP and completion of all required Day 1 procedures as outlined in Table 3; subsequent study days are consecutive calendar days. Every attempt should be made to administer 2 doses of study drug on Study Day 1. On Day 1, if q12h dosing is not feasible, the 1st and 2nd doses may be administered as close as 8 hours apart, in order to allow 2 doses to be given on Day 1. In this circumstance, the subject's dosing schedule should be adjusted on Day 2 to a regular q12h morning and evening schedule. Despite this, there may still be instances where it is not possible to administer 2 doses on Day 1. Subjects who receive only a single dose of study drug on Day 1 will receive their final dose in the morning on either Day 8 (to complete a 7-day course) or on Day 11 (to complete a 10-day course).

As described above, subjects randomized to the moxifloxacin treatment arm will receive IV moxifloxacin alternating with IV placebo to maintain the blind. Subjects should always receive active IV moxifloxacin as the first dose on Day 1. Subjects who begin therapy in the evening on Study Day 1 and whose schedule does not permit a second dose on Day 1 should have their dosing schedule adjusted on Day 2, so that active IV moxifloxacin is given as part of the morning dosing on all subsequent days.

Example 1: If a subject begins therapy at 3pm on Day 1, a second dose may be given at 11pm on Day 1. The subject's dosing schedule may then be adjusted on Day 2 to a regular q12h schedule (e.g., 8am and 8pm dosing). In this scenario, subjects randomized to moxifloxacin will receive active IV moxifloxacin at 3pm and IV matching placebo at 11pm on Day 1.

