Example 2: If a subject begins therapy at 5pm on Day 1, it is not possible to give a second dose on Day 1 within the 8 hour minimum between doses. Therefore, the subject will receive a single dose on Day 1, and then be adjusted on Day 2 to a regular q12h dosing schedule (e.g., 6am and 6pm dosing). In this scenario, subjects randomized to moxifloxacin will receive active IV moxifloxacin at 5pm on Day 1, active IV moxifloxacin again in the morning on Day 2 (e.g., 6am) and IV matching placebo in the evening on Day 2 (e.g., 6pm). Subjects who require a 7-day course of study drug and who receive only a single dose of study drug on Day 1 will receive their final dose in the morning on Day 8 (to complete a 7-day course). Subjects who require a 10-day course of study drug and who receive only a single dose of study drug on Day 1 will receive their final dose on Day 11 (to complete a 10-day course).

Oral study drug doses of lefamulin, linezolid or matching placebo are to be administered approximately q12h. Oral moxifloxacin (or matching placebo) should be administered approximately q24h. Oral moxifloxacin (or matching placebo for subjects in the lefamulin treatment arm) will always be given as part of the morning dosing.

Every effort should be made to maintain a q12h dosing schedule, about the same time each day. On days when this is not feasible, doses should be given within 4 hours of the scheduled dosing time (i.e., a minimum of 8 hours between doses).

Oral study drug should be administered at least 1 hour before a meal or 2 hours after a meal. However, in the event that a subject has taken any of the following – antacids containing aluminum, products containing iron, or multivitamins containing zinc – study drug should be administered 2 hours before or 4 hours after consuming any of these medications. Oral doses should be administered with approximately 240 mL (8 ounces) of water.

The lot numbers and expiration dates of all study drugs supplied will be recorded.

Infusions will be administered via an infusion set and IV catheter at a controlled rate over approximately 60 minutes.

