## 9.10 Pharmacokinetic Analyses

Measured plasma concentrations of lefamulin and BC-8041 will be summarized descriptively by treatment group and time point of collection. Summary statistics in the tabulation will include  $n$ , mean, standard deviation, CV [%], median, minimum and maximum.

Population PK modeling will be used to determine the individual model-predicted concentrations of lefamulin at least for Day 1 (PK/PD analysis). Additionally, plasma concentration time curves will be generated for day of IV/PO switch and PO treatment only. Simulation of model output will enable descriptive statistical analysis of PK variables such as the  $C_{max}$ ,  $C_{min}$  and AUC for lefamulin.

A description of the population PK analysis will be described in a separate SAP. Results of this analysis will be reported separately.

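### The last Day 3 IV PK sampling window overlaps the evening infusion, and nothing requires the draw to be pre-dose

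*Protocol*

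**What the plan says.** Section 6.13, Table 9, lists four samples around the Day 3 morning infusion. The last is due "8-12 h following the end of infusion". Table 3 footnote x gives the same window: "and at 8–12 h after the infusion". Neither adds that the sample must be taken before the next dose.

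Section 5.6 fixes the dosing clock. On the interval: "Blinded IV study drug (lefamulin, moxifloxacin, linezolid, and matching placebo) will be administered approximately every 12 hours". On infusion length: "Blinded IV lefamulin and moxifloxacin study drug doses will be infused over approximately 60 minutes". When the schedule cannot be kept, "doses should be given within 4 hours of the scheduled dosing time (i.e., a minimum of 8 hours between doses"; Table 3 footnote w repeats that tolerance.

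The Day 3 evening dose is still intravenous. Figure 1, note b, states: "All subjects will have IV treatment for a minimum of 3 days (6 doses".

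Section 9.10 says that measured plasma concentrations of lefamulin and BC-8041 "will be summarized descriptively by treatment group and time point of collection". It derives Cmax, Cmin and AUC from simulation of the population PK model. The note below Table 10 asks sites to record actual times for all IV doses and for PK draws.

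**The concern.** A window counted from the end of one infusion should close before the next infusion starts, unless the plan intends otherwise. This one does not close in time. A site drawing 11.5 h after the morning infusion ends, while the evening infusion is running, complies fully with Table 9, so no deviation would be raised.

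The output at stake is the 8-12 h row of the descriptive summary in Section 9.10. It would be read as a late-interval concentration, but it could contain values from the rising phase of the next dose or from shortly after its peak. That would raise the row's mean and coefficient of variation for a reason unrelated to lefamulin's disposition. Only lefamulin-arm samples are assayed (Section 6.13.2), and in that arm every 12-hourly infusion is active drug, so an overlapping draw does pick up new drug.

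**Working it through.** **Inputs.** Window: 8 to 12 h after the end of the morning infusion (Table 9; Table 3 footnote x). Infusion length d = 1 h, stated as approximate (Section 5.6). Interval between infusion starts τ = 12 h nominally, 8 h at minimum (Section 5.6). Half-life 8.6 to 11.8 h (Section 1.5.1), used only in step 4.

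**Step 1. The protocol's own minimum gap.** One dose moved 4 h early on a 12 h schedule gives 12 − 4 = 8 h, which matches the stated minimum.

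**Step 2. The Day 3 evening dose is IV.** With two doses on Day 1 it is IV dose 2 + 2 + 2 = 6. With one dose on Day 1 it is dose 1 + 2 + 2 = 5. At least 6 IV doses are required before an oral switch, so it is IV either way.

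**Step 3. Where the next infusion falls.** Counted from the end of the morning infusion, the next one starts at τ − d and ends at τ. Window time at or after its start is 12 − (τ − d) = 13 − τ hours, kept between 0 and 4.

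| τ (h) | Next infusion (h after end of morning infusion) | Window before it (h) | During (h) | After (h) | Share during or after |
|---|---|---|---|---|---|
| 13 or more | starts at 12 or later | 4 | 0 | 0 | 0% |
| 12 | 11 to 12 | 3 | 1 | 0 | 25% |
| 11 | 10 to 11 | 2 | 1 | 1 | 50% |
| 10 | 9 to 10 | 1 | 1 | 2 | 75% |
| 9 | 8 to 9 | 0 | 1 | 3 | 100% |
| 8 | 7 to 8 | 0 | 0 | 4 | 100% |

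On exact 12-hourly dosing the window closes as the evening infusion ends, so only draws during that infusion arise. Draws after it need a shortened interval.

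**Step 4. How different a mistimed value could be.** Assume one-compartment decline at steady state and exact 12-hourly dosing. The ratio of the concentration at the end of the evening infusion to that just before it is 2^(11 / half-life).

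- Half-life 11.8 h: 2^(11/11.8) = 1.91
- Half-life 8.6 h: 2^(11/8.6) = 2.43

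This applies only to a draw at 12 h, the very end of the window. The 0.5 h rapid distribution phase described in Section 1.5.1 would make the ratio at that instant larger.

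**Step 5. Is a pre-dose draw implied elsewhere?** The first row of Table 9 is tied to the coming morning infusion. The first row of Table 10 is likewise tied to the coming dose: "Within 1 h prior to 1 st morning dose of oral study drug". The 8-12 h row has no such tie.

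**The case against.** The case for leaving this alone is substantial, and most of it stands.

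- **Actual times are recorded.** A population PK model can place a draw correctly within or after the next infusion. This confines the problem largely to one descriptive table, which supports an additional objective (Section 2.3).
- **No trough is mislabelled.** A reader might infer that samples labelled as trough are contaminated. Table 9 does not call this sample a trough; the only Cmin label in Section 6.13 is on the oral pre-dose sample in Table 10.
- **It is not the only late information.** A reader might infer that each subject's clearance and AUC rest on this draw. Table 9 also has a sample within 1 h before the Day 3 morning infusion. That is an end-of-interval value, taken after about two days of dosing, when Section 1.5 says steady state is reached.
- **The larger shares are not typical.** They need evening doses given early, while Section 5.6 asks for every effort to keep to 12 h. The same tolerance can lengthen the interval, and from 13 h there is no overlap. A share of the window is not a share of samples, and the ratio of 1.9 to 2.4 does not carry over to shortened intervals.
- **Detail may sit elsewhere.** Section 6.13.1 refers further collection instructions to a site study manual, and handling of mistimed samples is ordinary SAP content. Silence on exclusion in Section 9.10 is therefore not a defect in itself.

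None of this changes the window printed in the protocol, which permits the overlapping draw.

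**Conclusion.** The point holds at minor priority. The sampling window and the dosing clock conflict on the protocol's own figures: 1 h of 4 on exact 12-hourly dosing, and up to the whole window at the shortest permitted gaps. The arithmetic takes the infusion as exactly 60 minutes. On 12-hourly dosing the overlap equals the infusion length, so a somewhat longer or shorter infusion changes its size but does not remove it.

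How many samples would actually be affected cannot be told from the protocol, because it depends on when sites draw within the window. The consequence is a possible mixture in one row of the by-time-point summary. The documents do not support any claim about bias in model-based exposure, and no efficacy or safety conclusion is touched.

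**What to change.** In Table 9 and Table 3 footnote x, state that the last sample is drawn before the start of the evening infusion, nominally 8 to 11 h after the end of the morning infusion, or just before the evening infusion if that starts earlier. The last clause is needed: at an 8 h gap the evening infusion starts 7 h after the morning one ends, so a strict 8 to 11 h pre-dose window could not be met.

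In Section 9.10, add one sentence: samples drawn after the next infusion began are left out of the by-time-point summary and kept in the population PK dataset at their actual times.

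The cost is one line in each of two places and one sentence in a third. There are no extra samples and no change to dosing. The downside is a slightly narrower sampling window for sites.

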### 6.13.1 Sample Collection Methodology

Blood samples for PK analysis will be collected from a vein in the opposite arm from the arm in which infusion is given into tubes containing K3EDTA, immediately chilled on crushed ice, and then centrifuged to separate plasma. Promptly following centrifugation, plasma specimens will be immediately deep frozen and stored at -20°C or cooler until transported. The total time period from blood withdrawal to storage of plasma at -20°C should not exceed 60 minutes.

Additional information and instructions for blood sample collection is provided in the investigative site study manual.

### 6.13.2 Assay Methodology

Plasma samples from subjects who received lefamulin will be analyzed for the concentration of lefamulin and its major metabolite, BC-8041, using a validated liquid chromatography-tandem mass spectrometry method at the bioanalytical laboratory. Samples from subjects who did not receive lefamulin (i.e., received the comparator) will not be analyzed. Scientists at the bioanalytical laboratory will be unblinded before bioanalysis.

## 6.14 Microbiological Assessment

The following microbiological assessments will be performed at the time points described in Table 3. Details regarding storage of samples and shipment to the central laboratory can be found in the Laboratory Manual.

### 6.14.1 Sputum Samples

- A sputum sample will be taken at Screening for Gram's staining, culture and susceptibility testing at the local/regional laboratory. If a subject is unable to produce an adequate sputum sample at Screening, a specimen may be obtained within 24 hours after the first dose of study drug. Gram's stain and culture results from the local/regional laboratory will be recorded in the eCRF.
- If possible, subjects who are discontinued from study drug due to clinical failure should have repeat cultures collected for microbiologic culture prior to switching to alternate appropriate therapy.
- To be adequate, Gram's stains of sputum samples should have >25 polymorphonuclear (PMN) cells **AND** <10 squamous epithelial cells per LPF. A repeat sample may be taken

if these criteria are not met. Sputum samples will only be taken at subsequent visits when clinically indicated.

- All organisms isolated from sputum samples which are not considered contaminants will be sent to the central laboratory for confirmatory identification and susceptibility testing. The following organisms, if isolated, will always be sent to the central laboratory for confirmatory identification and susceptibility testing: *S. pneumoniae*, *S. aureus*, *S. pyogenes*, *Haemophilus* spp., *M. catarrhalis*, *L. pneumophila*, *C. pneumoniae*, and *M. pneumoniae*. Further details regarding organisms which should be sent to the central microbiology laboratory, including a list of organisms which if isolated will be classified as contaminants, can be found in the Laboratory Manual.
- Gram's stain slides will be sent to the central laboratory for a confirmatory reading. The stained slide read by the local/regional laboratory as well as an unstained slide will be sent to the central laboratory.
- A portion of each Screening sputum sample taken will be frozen until shipment to the central laboratory. Frozen samples will be analyzed by the central microbiological laboratory using real-time PCR for common CABP pathogens. Additionally, for subjects who have a positive urinary antigen test for *Legionella* spp. the frozen sputum will be utilized for *L. pneumophila* isolation and susceptibility testing.

#### 6.14.2 Bronchoalveolar Lavage Samples (BAL)

A BAL sample will be collected only if clinically indicated and sent to the local/regional laboratory for Gram's staining, culture and susceptibility testing. Repeat BAL samples will not be required. However, if the subject undergoes a repeat bronchoscopy as clinically warranted, a repeat BAL sample should be sent for Gram's staining and culture. All organisms isolated from BAL samples, which are not considered contaminants, will be sent to the central laboratory for confirmatory identification and susceptibility testing. Culture results from the local/regional laboratory will be recorded in the eCRF.

#### 6.14.3 Pleural Fluid Samples

A pleural fluid sample will be collected only if clinically indicated and sent to the local/regional laboratory for Gram's staining, culture and susceptibility testing. Repeat pleural fluid samples will not be required. However, if the subject undergoes a repeat thoracentesis as clinically warranted, a repeat pleural fluid sample should be sent for Gram's staining and culture. If possible, pleural fluid samples should be incubated in blood culture bottles for optimal pathogen recovery. All organisms isolated from pleural fluid samples which are not considered contaminants will be sent to the central laboratory for confirmatory identification and susceptibility testing. Culture results from the local/regional laboratory will be recorded in the eCRF.

